4.4 Medical validation of programmed overall lesion response

In order to be as objective as possible the RECIST programmed calculated response assessment is very strict regarding measurement methods (i.e. any assessment with more or less sensitive method than the one used to assess the lesion at baseline is considered UNK) and not available evaluations (i.e. if any target or non-target lesion was not evaluated the whole overall lesion response is UNK unless remaining lesions qualified for PD). This contrasts with the slightly more flexible guidance given to local investigators (and to the central reviewers) to use expert judgment in determining response in these type of situations, and therefore as a consequence discrepancies between the different sources of response assessment often arise. To ensure the quality of response assessments from the local site and/or the central reviewer, the responses may be re-evaluated by clinicians (based on local investigator data recorded in eCRF or based on central reviewer data entered in the database) at Novartis or external experts. In addition, data review reports will be available to identify assessments for which the investigators' or central reader's opinion does not match the programmed calculated response based on RECIST criteria. This may be queried for clarification. However, the investigator or central reader's response assessment will never be overruled.

If Novartis elect to invalidate an overall lesion response as evaluated by the investigator or central reader upon internal or external review of the data, the calculated overall lesion response at that specific assessment is to be kept in a dataset. This must be clearly documented in the RAP documentation and agreed before database lock. This dataset should be created and stored as part of the 'raw' data.

Any discontinuation due to 'Disease progression' without documentation of progression by RECIST criteria should be carefully reviewed. Only patients with documented deterioration of symptoms indicative of progression of disease should have this reason for discontinuation of treatment or study evaluation.

4.5 Programming rules

The following should be used for programming of efficacy results:

4.5.1 Calculation of 'time to event' variables

Time to event = end date - start date + 1 (in days)

When no post-baseline tumor assessments are available, the date of randomization/start of treatment will be used as end date (duration = 1 day) when time is to be censored at last tumor assessment, i.e. time to event variables can never be negative.

4.5.2 Incomplete assessment dates

All investigation dates (e.g., X-ray, CT scan) must be completed with day, month and year.

If one or more investigation dates are incomplete but other investigation dates are available, this/these incomplete date(s) are not considered for calculation of the assessment date (and assessment date is calculated as outlined in [Section 3.2.7](#)). If all measurement dates have no day recorded, the 1st of the month is used.

If the month is not completed, for any of the investigations, the respective assessment will be considered to be at the date which is exactly between previous and following assessment. If a previous and following assessment is not available, this assessment will not be used for any calculation.

4.5.3 Incomplete dates for last known date patient alive or death

All dates must be completed with day, month and year. If the day is missing, the 15th of the month will be used for incomplete death dates or dates of last contact.

4.5.4 Non-target lesion response

If no non-target lesions are identified at baseline (and therefore not followed throughout the study), the non-target lesion response at each assessment will be considered 'not applicable (NA)'.

4.5.5 Study/project specific programming

The standard analysis programs need to be adapted for each study/project.

4.5.6 Censoring reason

In order to summarize the various reasons for censoring, the following categories will be calculated for each time to event variable based on the treatment completion page, the study evaluation completion page and the survival page.

For survival the following censoring reasons are possible:

- Alive
- Lost to follow-up

For PFS and TTP (and therefore duration of responses) the following censoring reasons are possible:

- Ongoing without event
- Lost to follow-up
- Withdraw consent
- Adequate assessment no longer available*
- Event documented after two or more missing tumor assessments (optional, see [Table 3-2](#))
- Death due to reason other than underlying cancer (*only used for TTP and duration of response*)
- Initiation of new anti-cancer therapy

* Adequate assessment is defined in [Section 3.2.7](#). This reason is applicable when adequate evaluations are missing for a specified period prior to data cut-off (or prior to any other censoring reason) corresponding to the unavailability of two or more planned tumor assessments prior to the cut-off date. The following clarifications concerning this reason should also be noted:

- This may be when there has been a definite decision to stop evaluation (e.g., reason=“Sponsor decision” on study evaluation completion page), when patients are not followed for progression after treatment completion or when only UNK assessments are available just prior to data cut-off).
- The reason "Adequate assessment no longer available" also prevails in situations when another censoring reason (e.g., withdrawal of consent, lost to follow-up or alternative anti-cancer therapy) has occurred more than the specified period following the last adequate assessment.
- This reason will also be used to censor in case of no baseline assessment.

5 References (available upon request)

- Dent S, Zee (2001) application of a new multinomial phase II stopping rule using response and early progression, *J Clin Oncol*; 19: 785-791
- Eisenhauer E, et al (2009) New response evaluation criteria in solid tumors: revised RECIST guideline (version 1.1). *European Journal of Cancer*, Vol.45: 228-47
- Ellis S, et al (2008) Analysis of duration of response in oncology trials. *Contemp Clin Trials* 2008; 29: 456-465
- EMA Guidance: 2012 Guideline on the evaluation of anticancer medicinal products in man
- FDA Guidelines: 2005 Clinical Trial Endpoints for the Approval of Cancer Drugs and Biologics, April 2005

LPFV	Last Patient First Visit
LPLV	Last Patient Last Visit

LVEF	Left Ventricular Ejection Fraction
MedDRA	Medical Dictionary for Regulatory Activities
mRCC	Metastatic Renal Cell Carcinoma
MRI	Magnetic Resonance Imaging
MSKCC	Memorial Sloan Kettering Cancer Center
MUGA	Multigated Acquisition Scan
NCI	National Cancer Institute
o.d.	Once Daily
ORR	Overall Response Rate
OS	Overall Survival
PD	Progression Disease
PDI	Planned Dose Intensity
PFS	Progression-Free Survival
PPS	Per-Protocol Set
PR	Partial Response
PRO	Patient-reported Outcomes
PT	Preferred Term
qd	Quaque die / once a day
QoL	Quality of Life
RAP	Report and Analysis Process
RCC	Renal Cell Carcinoma
RDI	Relative Dose Intensity
RECIST	Response Evaluation Criteria in Solid Tumors
SAE	Serious Adverse Event
SAP	Statistical Analysis Plan
SAS	Statistical Analysis System
SD	Stable Disease
SOC	System Organ Class
TBL	Total Bilirubin
TFLs	Tables, Figures, Listings
ULOQ	Upper Limit of Quantification
UNK	Unknown
WBC	White Blood Cell
WHO	World Health Organization

1 Introduction

This statistical analysis plan (SAP) describes all planned analyses for the clinical study report(s) (CSR) of study CPZP034A2410, a prospective international multicenter phase II study to evaluate the efficacy, safety and quality of life of oral daily pazopanib in patients with advanced and/or metastatic renal cell carcinoma after previous therapy with checkpoint inhibitor treatment.

The content of this SAP is based on protocol PZP034A2410 v01. All decisions regarding final analysis, as defined in the SAP document, have been made prior to database lock of the study data.

1.1 Study design

This is a multi-center, open-label, single-arm phase II study to determine the efficacy, safety and quality of life of treatment with pazopanib in patients with advanced and/or metastatic renal cell carcinoma (RCC) following prior treatment with immune checkpoint inhibitors. A total of approximately 100 patients are planned to be enrolled (with an approximately 40 patients receive pazopanib as 2nd line treatment.) and treated in this study.

Patients will receive standard dose of pazopanib daily until disease progression, unacceptable toxicity, death, pregnancy, start of a new anti-neoplastic therapy, discontinuation at the discretion of the investigator or patient, lost to follow-up, end of study or study is terminated by the sponsor, whichever comes first. Dose modifications will be allowed for patients who do not tolerate the standard starting dose of 800 mg daily. Patients will be followed for survival (except if consent is withdrawn or patient is lost to follow-up).

[figure not shown]
Progression free survival (PFS) as assessed by local investigator review of tumor assessments and using RECIST v1.1 criteria is the primary endpoint in this study.

The primary analysis for PFS is planned after all patients have received a minimum of 6 cycles of study treatment or have discontinued study treatment early.

No formal interim analysis is planned for this trial.

The cut-off date for the primary analysis will be established after all patients have received a minimum of 6 cycles of study treatment or have discontinued study treatment early. The primary analysis data will be summarized in the primary clinical study report (CSR).

Figure 1-1 Study design

1.2 Study objectives and endpoints

Objectives and related endpoints are described in [Table 1-1](#) below.

Table 1-1 Objectives and related endpoints

Objective	Endpoint
Primary	
To assess the progression free survival (PFS) based on local investigator assessment	PFS based on local investigator assessment using RECIST v1.1 defined as the time from the first administration of study treatment until the first documented progressive disease (PD) or death due to any cause.
Secondary	
To assess overall response rate (ORR) and clinical benefit rate (CBR) based on local investigator assessment	ORR defined as the proportion of patients with best overall response of confirmed complete response (CR) or partial response (PR) based on local investigator's assessment according to RECIST v1.1 CBR defined as the proportion of patients with a best overall response of CR or PR or an overall lesion response of stable disease (SD), or Non-CR/Non-PD lasting \geq 24 weeks based on local investigator's assessment according to RECIST v1.1.
To assess overall survival (OS)	Overall survival (OS) defined as the time from the first administration of study treatment until death due to any cause.
To assess duration of response (DOR) in patients with CR or PR	DOR defined as the time from the date of first documented response (confirmed CR or PR) to the date of tumor progression.
To evaluate the safety and tolerability	Type, frequency and severity of AEs per NCI-CTCAE v4.03. Type, frequency and severity of laboratory toxicities per NCI-CTCAE v4.03.
To assess quality of life	Quality of life as assessed by the EuroQoL EQ-5D-5L and FKSI-DRS health questionnaires.

2 Statistical methods

2.1 Data analysis general information

The primary and final analyses will be performed by Novartis and/or a designated CRO. SAS version 9.4 or later software will be used to perform all data analyses and to generate tables, figures and listings.

Data included in the analysis

The cut-off date for the primary analysis of study data will be established after all enrolled patients have completed 6 cycles of treatment or have discontinued study. The final analysis cut-off date will be established 2 years after the last patient has started treatment. All statistical analyses will be performed using all data collected in the database up to the data cut-off date. All data with an assessment date or event start date (e.g. vital sign assessment date or start date of an adverse event) prior to or on the cut-off date will be included in the analysis. Any data collected beyond the cut-off date will not be included in the analysis and will not be used for any derivations.

All events with start date before or on the cut-off date and end date after the cut-off date will be reported as 'ongoing'. The same rule will be applied to events starting before or on the cut-off date and not having documented end date. This approach applies, in particular, to adverse event and concomitant medication reports. For these events, the end date will not be imputed and therefore will not appear in the listings.

General analysis conventions

Pooling of centers: Unless specified otherwise, data from all study centers will be pooled for the analysis. Due to expected small number of patients enrolled at centers, no center effect will be assessed.

Qualitative data (e.g., gender, race, etc.) will be summarized by means of contingency tables; a missing category will be included as applicable. Percentages will be calculated using the number of patients in the relevant population or subgroup as the denominator.

Quantitative data (e.g., age, body weight, etc.) will be summarized by appropriate descriptive statistics (i.e. mean, standard deviation, median, minimum, and maximum and in addition when specified 25th and 75th percentiles).

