Investigational drug	The study treatment whose properties are being tested in the study; this definition is consistent with US CFR 21 Section 312.3 and is synonymous with "investigational new drug."
Investigational treatment	Drug whose properties are being tested in the study as well as their associated placebo and active treatment controls (when applicable). This also includes approved drugs used outside of their indication/approved dosage, or that are tested in a fixed combination. Investigational treatment generally does not include other study treatments administered as concomitant background therapy required or allowed by the protocol when used in within approved indication/dosage
Medication number	A unique identifier on the label of each study treatment package which is linked to one of the treatment groups of a study
Other study treatment	Any drug administered to the patient as part of the required study procedures that was not included in the investigational treatment
Subject Number (Subject No.)	A unique identifying number assigned to each patient/subject/healthy volunteer who enrolls in the study
Study treatment	Includes any drug or combination of drugs in any study arm administered to the patient (subject) as part of the required study procedures, including placebo and active drug run-ins. In specific examples, it is important to judge investigational treatment component relationship relative to a study treatment combination; study treatment in this case refers to the investigational and non-investigational treatments in combination.
Study treatment discontinuation	Point/time when patient permanently stops taking study treatment for any reason
Variable	Identifier used in the data analysis; derived directly or indirectly from data collected using specified assessments at specified timepoints
Withdrawal of consent	Withdrawal of consent occurs only when a patient does not want to participate in the study any longer, and does not want any further visits or assessments, and does not want any further study related contact

Amendment 2 (14-Sep-2020)

Amendment rationale

As of amendment date, 8 patients remain on study treatment in two countries (Chile-2 sites and France-1 site).

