4.3 Definition of end of study

The end of study will occur 2 years after the last patient is enrolled, or when all patients have died or discontinued from the study and are no longer being followed for survival, whichever occurs first. All available data from all patients will be analyzed and summarized in a final CSR.

Patients who are still deriving benefit from the treatment at the end of the study, in the opinion of the investigator, should be switched to a local prescription in case Votrient is commercially available and reimbursed in that country. For countries in which Votrient is not reimbursed, nor commercially available or for patients who cannot afford treatment, Novartis will make every effort to continue to provide treatment with pazopanib through another program per local regulations.

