6.1.2 Treatment duration

Patients may continue on study treatment until 2 years after the last patient is enrolled. Patients may be discontinued from treatment with study drug earlier due to unacceptable toxicity, disease progression and/or treatment discontinuation at the discretion of the investigator or the patient. For patients, who in the opinion of the investigator are still deriving clinical benefit from pazopanib, every effort will be made to continue provision of study treatment through another program.

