7.1.5 Follow-up phases

7.1.5.1 Safety follow-up

All patients must have safety evaluations for 30 days after the last dose of study treatment.

Data collected should be added to the Adverse Events eCRF, the Surgical and Medical Procedures eCRF, the Concomitant Medications eCRF and the “Antineoplastic Therapy Since Discontinuation of Study Treatment” eCRF for the first antineoplastic therapy to be administered to the patient since study drug discontinuation.

Patients whose treatment is interrupted or permanently discontinued due to an adverse event, including abnormal laboratory value, must be followed until resolution or stabilization of the event, whichever comes first. If patients refuse to return for safety evaluation visits or are unable to do so, every effort should be made to contact them by telephone to determine their status. Attempts to contact the patient should be documented in the source documents (e.g., dates of telephone calls, registered letters, etc.).

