The primary efficacy and safety analyses will be conducted after all patients have completed 6 cycles of study treatment or have discontinued early. The primary analysis will be summarized in the primary CSR based on the Full Analysis Set (FAS). The final analysis will be performed at the end of the study and will be summarized in the final study CSR. Data analysis cut-off dates will be determined and the primary and the final analyses, and all data captured in the study up to the respective cut-off date will be analyzed and reported.

- The primary efficacy and selected safety analyses will also be performed for the following subgroups:
- Line of therapy (2nd / 3rd).

- 2nd line therapy: all patients who received only one line of prior antineoplastic therapy before the start of study treatment
- 3rd line therapy: all patients who received two lines of prior antineoplastic therapy before the start of study treatment (treatment with immune checkpoint inhibitor must have been the last treatment prior to study entry)
- Age category
- MSKCC and IMDC risk groups

Further details will be included in the Statistical Analysis Plan (SAP).

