2. **on-treatment period:** from date of first administration of study treatment to 30 days after date of last actual administration of any study treatment (including start and stop date)
3. **post-treatment period:** starting at day 30+1 after last administration of study treatment.

Safety summaries (tables, figures) include only data from the on-treatment period with the exception of baseline data which will also be summarized where appropriate (e.g. change from baseline summaries). In addition, a separate summary for death including on-treatment and post-treatment deaths will be provided. In particular, summary tables for adverse events (AEs) will summarize only on-treatment events, with a start date during the on-treatment period (**treatment-emergent** AEs).

However, all safety data (including those from the post-treatment period) will be listed and those collected during the pre-treatment and post-treatment period will be flagged.

Windows for multiple assessments of PRO

In order to summarize PRO measures and performance status (PS) collected over time (including unscheduled visits), the assessments will be time slotted. The following general rule will be applied in creating the assessment windows: If more than one assessment is done within the same time window, the assessment performed closest to the target date will be used. If two assessments within a time window are equidistant from the target date, then the worst of the two assessments will be used. If multiple assessments on the same date then the worst case will be used. Data obtained at the end of treatment will be classified as other assessment in the corresponding time window. Data from all assessments (scheduled and unscheduled), including multiple assessments, will be listed.

Note that only data collected under treatment (i.e. while the patient is treated) will be included in the time to definitive deterioration. The end of treatment assessment will be included if collected within 30 days of the last dose intake.

Table 2-1 Time windows for EQ-5D-5L, KPS and FKSI-DRS assessments

Assessment	Target day of	Time Interval
Baseline		≤ Day 1
Cycle 2 Day 1	29	Day 2 to day 42
Cycle 3 Day 1	57	Day 43 to day 70
Cycle 4 Day 1	85	Day 71 to day 98
Cycle 5 Day 1	113	Day 99 to day 126
Cycle 6 Day 1	141	Day 127 to day 154
Cycle 7 Day 1	169	Day 155 to day 196
Cycle 9 Day 1	225	Day 197 to day 252
Cycle 11 Day 1	281	Day 253 to day 308
Cycle 13 Day 1	337	Day 309 to day 378

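### For the few patients on pazopanib at or near the two-year point, the final SAP cut-off excludes some or all of the 30-day safety window that both documents count as on-treatment time

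*SAP*

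**What the plan says.** **Dosing limit.** Protocol 6.1.2: "Patients may continue on study treatment until 2 years after the last patient is enrolled". Protocol 7.1.2 repeats this, and the protocol summary gives the same limit from LPFV.

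**Study end.** Protocol 4.3: "The end of study will occur 2 years after the last patient is enrolled", or earlier if nobody is still being followed. Protocol 7.1.5.3 equates study end with LPFV plus two years.

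**Final cut-off.** SAP 2.1: "The final analysis cut-off date will be established 2 years after the last patient has started treatment". The same section adds: "Any data collected beyond the cut-off date will not be included in the analysis and will not be used for any derivations". An adverse event is included or excluded by its start date. The opening of Protocol Section 10 has the matching rule that "all data captured in the study up to the respective cut-off date will be analyzed and reported".

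**Safety follow-up.** Protocol 7.1.5.1: "All patients must have safety evaluations for 30 days after the last dose of study treatment".

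**On-treatment period.** SAP 2.1.1 defines it as running "from date of first administration of study treatment to 30 days after date of last actual administration of any study treatment". Protocol 10.5.3.1 and SAP 2.8 use the same 30 days, and the adverse event tables are built on this period.

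**The concern.** For a patient dosed up to the limit, the 30 days after the last dose are on-treatment time by definition and must be followed, but they start at about the date after which the SAP admits no data. A patient who stops shortly before that date loses part of the window.

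The final safety tables would then fall short of the period they define. Adverse events, SAEs, AESIs, laboratory abnormalities and on-treatment deaths arising in the lost days would be missing from the final CSR. The patients concerned would still be in the denominators, because SAP 2.1 bases percentages on the whole relevant population. They are also patients who stayed on the drug to the end of the study. A window cut at the primary cut-off can be completed in the final CSR; one cut at the final cut-off cannot.

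**Working it through.** **1. Date arithmetic.** Let g be the number of days from the last patient's enrolment (or LPFV) to that patient's first dose.

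- Last permitted dose = enrolment + 2 years.
- Study end = enrolment + 2 years, so it is 0 days after the last permitted dose under either meaning of enrolment.
- Final cut-off = first dose + 2 years, which is g days after the last permitted dose.
- Follow-up days captured = min(30, g); days lost = 30 − min(30, g).

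The documents support two readings of g. Protocol 6.4.2 has patients enrolled through the IRT before dosing, which puts g near 0. Protocol 6.4.1 speaks of enrolment at screening, and Protocol 7.1.1 lets screening start up to 28 days before treatment, so g could reach 28.

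| g (days) | Captured | Lost |
|---|---|---|
| 0 | 0 | 30 |
| 3 | 3 | 27 |
| 7 | 7 | 23 |
| 28 | 28 | 2 |

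Only a gap of 30 days or more, for example after re-screening, would capture the whole window.

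**2. Does another passage repair it?**

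- SAP Table 5-2 uses last dose plus 30 days when imputing end dates, but caps it at the cut-off. That confirms the truncation.
- SAP 5.1.1 expects every end-of-treatment page before final lock. That page does not cover the 30-day follow-up.
- Protocol 4.3 promises a final CSR on all available data, but names no later safety cut-off and does not displace the explicit SAP rule.
- SAP 2.1.1 promises listings that include post-treatment data, but SAP 2.1 makes no exception for listings.

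**3. How many patients?** First, the planning model is checked against the plan's own table. Inputs from Protocol 10.8: 12 months of accrual and 6 months of follow-up after LPFV. I assume exponential PFS and uniform accrual, with λ = ln 2 / median.

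- Expected events: d = N[1 − (e^(−6λ) − e^(−18λ))/(12λ)]
- 95% CI: median × exp(±1.96/√d)
- Median 5, N = 100: d = 78.8, CI 4.01 to 6.24, width 2.23, as in Table 10-1. The other eight rows also reproduce.

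The same model, with treatment assumed to last until the PFS event, gives the share still on drug 24 months after LPFV:

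p = (e^(−24λ) − e^(−36λ))/(12λ)

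| Median (months) | Still on drug, per 100 | Stopped in the preceding 30 days, per 100 |
|---|---|---|
| 4 | 0.66 | 0.12 |
| 5 | 1.75 | 0.26 |
| 6 | 3.38 | 0.41 |

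For median 6: (0.0625 − 0.015625)/1.3863 = 0.0338.

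**4. Share of on-treatment time.** At median 5 months, mean time on drug is 5/ln 2 = 7.21 months, about 220 days. With the 30-day window, 100 patients contribute about 100 × 250 = 25,000 days. At g = 0 the loss from patients still on drug is 1.75 × 30 = 52.5 days, about 0.2%.

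**The case against.** The strongest case against is as follows.

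- **The anchors differ.** A reader might infer that the cut-off falls exactly on the last dosing day, so that the whole window is always lost. The documents do not establish that. The coincidence is certain only for study end; for the cut-off the loss runs from about 2 to 30 days. This stands.
- **Collection is not analysis.** A reader might infer that the rules cannot all be obeyed, or that safety data are thrown away. Sites can follow every patient while the SAP analyses to a fixed date, and Protocol 8.2.2 still sends SAEs to the sponsor for at least 30 days after the last dose. The gap is in the final tables and listings. The one direct tension over conduct is that Protocol 4.3 ends the study before follow-up required by 7.1.5.1 can finish. This stands.
- **Truncation is an ordinary convention.** SAP Table 5-2 caps at the cut-off, the primary analysis truncates in the same way, and crude incidence with unequal follow-up is how all the adverse event tables work. That is fair, but it does not justify truncating at the last analysis, where the missing days are already due to be collected.
- **Some of these patients may continue pazopanib** by local prescription or another program (Protocol 4.3), so their 30 days may not be drug-free. That affects interpretation; no passage exempts them from follow-up.
- **The effect is small.** This stands, and it limits the weight of the point.

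**Conclusion.** The point holds, at modest size. As written, the final safety tables cannot cover the on-treatment period that both documents define for patients on pazopanib at the two-year point or stopping within 30 days before it. Each patient dosed to the limit loses about 30 days if enrolment and first dose coincide, and about 2 days if enrolment is a screening visit 28 days earlier.

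About 0.7 to 3.4 patients per 100 would still be on drug under medians of 4 to 6 months, with a further 0.1 to 0.4 partly affected. This assumes exponential PFS, uniform 12-month accrual and treatment until the PFS event. Stopping earlier for toxicity or choice would lower these figures; a longer PFS tail would raise them.

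The Amendment 2 rationale records that "8 patients remain on study treatment in two countries". A reader might infer that eight patients and 8 × 30 = 240 patient-days are lost. That does not follow: the count is dated 14-Sep-2020, and neither the actual cut-off date nor the number on drug at that date is given.

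PFS is unaffected, and so is SAE reporting to the sponsor. The change is still worth making, because the loss is final once the database is locked and the remedy is cheap.

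**What to change.** - **SAP 2.1.** Set the final cut-off for safety data (AEs, SAEs, AESIs, laboratory data, on-treatment deaths) at the later of two years after the last patient's first dose and completion of the 30-day safety follow-up of the last patient to stop study treatment. Efficacy may keep the two-year cut-off. Footnote any death that appears in the safety table but falls after the OS cut-off.
- **Anchor.** Use one defined date wherever the documents now refer to enrolment, LPFV or start of treatment. This alone does not close the gap: if every rule ran from first dose, the full 30 days would be lost.
- **Protocol 4.3 and 7.1.5.1.** Reconcile them so that study end leaves room for the 30-day follow-up. Keep the existing clause that ends the study early when nobody is still followed; a plain later-of rule for study end would remove it.

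**Cost.** Final lock moves by up to about 30 days. No visits are added, since the follow-up is already mandatory. The Protocol 4.3 wording needs a written amendment with the approvals in Protocol 12.1. No change to dosing is proposed.

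If the sponsor keeps the single cut-off, the SAP should at least say that the window is truncated for these patients, and the CSR should report how many there are.
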